5.2.1.1.2 Part A – ADXS31-142 Monotherapy

Part A of the trial completed. The ADXS31-142 monotherapy doses that were to be used in this trial are outlined below in [Table 6](#). The starting dose level of ADXS31-142 monotherapy in Part A is 1×10^9 cfu (DL 1). The dose was to be escalated, remain the same or be de-escalated based on interim safety data review from other Advaxis trials at a particular dose level or according to pre-defined DLT criteria (see [Section 5.2.1.1.1](#)) in accordance with the mTPI design (see [Table 5](#)), and after consultation with the Sponsor and Investigator, until the RP2D is selected. However, based on safety data from other Advaxis trials that use similar constructs, it was decided that escalation to 5×10^9 cfu or 1×10^{10} cfu would no longer be included in this study design. This is based on overall review of the safety data across the Lm-based program of clinical trials, which established that the starting dose of 1×10^9 cfu is more tolerable than higher doses.

Table 6 ADXS31-142 Monotherapy Doses to be used in Part A

Dose Level	Dose	Route of Administration	Regimen
1	1×10^9 cfu	IV infusion	Day 1 of Weeks 1, 4 and 7 of 12-week cycle
2	5×10^9 cfu	IV infusion	Day 1 of Weeks 1, 4 and 7 of 12-week cycle
3	1×10^{10} cfu	IV infusion	Day 1 of Weeks 1, 4 and 7 of 12-week cycle
-1	$.5 \times 10^9$ cfu	IV infusion	Day 1 of Weeks 1, 4 and 7 of 12-week cycle

5.2.1.1.3 Part B – ADXS31-142 + Pembrolizumab (MK-3475) Combination Therapy

Part B consists of a modified 3+3 design to identify a recommended RP2D of the combination which will be used in the Part B expansion phase. The starting ADXS31-142 dose for Part B will be the RP2D determined in Part A. For example, if 1×10^9 cfu is determined to be the RP2D in Part A then that will be the starting dose. The ADXS31-142 dose will not be escalated in Part B. However, if the ADXS31-142 dose of 1×10^9 cfu (Dose Level 1) isn't tolerable in combination, then the dose of ADXS31-142 will be de-escalated to a dose of 0.5×10^9 cfu (Dose Level -1) in combination with pembrolizumab (MK-3475) 200 mg.

Interim safety data review and/or DLTs observed at the first dose level will be used to determine the need for de-escalation to the next lower dose level. Determination to dose de-escalate will be made according to a modified 3+3 design as follows:

An initial cohort of 3 subjects will be enrolled at doses of ADXS31-142 1×10^9 cfu in combination with pembrolizumab (MK-3475) 200 mg.

- If 0/3 subjects develop a DLT,
 - Another 3 subjects will be enrolled at this dose level.
 - If 0, 1 or 2 of the 3 new subjects develops a DLT (for a total of 0/6, 1/6 or 2/6 subjects with a DLT at this dose level), the current dose will be considered the RP2D and the trial will proceed to the dose expansion stage.
 - If 3 of the 3 new subjects develop a DLT (for a total of 3/6 subjects with a DLT at this dose level), the dose will be de-escalated to DL -1 and a dose of ADXS31-142 0.5×10^9 will be administered in combination with pembrolizumab (MK-3475) 200 mg.
- If 1/3 subjects develop a DLT,
 - Another 3 subjects will be enrolled at this dose level.
 - If 0 or 1 of the 3 new subjects develops a DLT (for a total of 1/6 or 2/6 subjects with a DLT at this dose level), the current dose will be considered

the recommended MTD, and the trial will proceed to the dose expansion stage.

- If >1 of the 3 new subjects develop a DLT (for a total of >2/6 subjects with a DLT at this dose level), the dose will be de-escalated to DL -1 of ADXS31-142 0.5×10^9 in combination with pembrolizumab (MK-3475) 200 mg.
- If 2/3 or 3/3 subjects develops a DLT the dose will be de-escalated.

If, following the rules above the dose is de-escalated, the 3 + 3 rules above will be repeated. Should additional de-escalation be required, a dose lower than 0.5×10^9 may be considered or the Sponsor may decide to take other action (e.g., stop the trial) based on a comprehensive review of the data from this trial as well as other trials.

This protocol will also allow de-escalation to an intermediate, not pre-defined and not previously-studied dose, if evaluation of toxicity at such a dose is desired in lieu of proceeding directly to the dose expansion stage of the trial.

Table 7 ADXS31-142 and Pembrolizumab (MK-3475) Combination Therapy Doses to be used in Trial Part B

Drug	Dose Level	Dose	Route of Administration	Regimen
ADXS31-142	11	1×10^9	IV infusion	Day 1 of Weeks 1, 4 and 7 of 12-week cycle
	-1	0.5×10^9	IV infusion	Day 1 of Weeks 1, 4 and 7 of 12-week cycle
Pembrolizumab (MK-3475)		200 mg	IV infusion	Day 1 Q3W of 12-week cycle

Cohort Expansion: Once the RP2D is decided, an additional cohort of subjects will be enrolled at the selected RP2D for combination therapy. The number of subjects will depend on the number of subjects previously treated in the dose-finding portion. It is planned to treat a total of approximately 30 subjects at the RP2D. Subjects will be enrolled on a rolling basis.

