2.1.2 Part B – ADXS31-142 + Pembrolizumab (MK-3475) Combination Therapy

Part B of the study will be an open-label, Phase 1-2, multicenter, non-randomized dose-determining trial of ADXS31-142 in combination with pembrolizumab (MK-3475) in subjects with mCRPC. Part B will consist of a dose-determination phase followed by an expansion cohort phase. The dose-determination phase is intended to select a RP2D for the combination. A modified 3+3 design will be used to determine the dose of ADXS31-142 in combination with pembrolizumab (MK-3475).

[figure not shown]
During the dose-determining stage, subjects will be entered at a dose of 1×10^9 of ADXS31-142 (see [Table 7](#)) in combination with pembrolizumab (MK-3475) at 200 mg. If this dose combination is not tolerable, then Dose Level -1 at a dose of 0.5×10^9 of ADXS31-142 in combination with pembrolizumab (MK-3475) at a dose of 200 mg will be evaluated. Dose-determination will continue until identification of a recommended RP2D for the combination to be used in the expansion cohort. A minimum of 6 subjects will be treated at the RP2D before initiating the expansion cohort.

The expansion cohort will be open for enrollment once the RP2D of ADXS31-142 in combination with pembrolizumab (MK-3475) is selected in the Part B dose-determination phase. Further assessment of the RP2D will be explored in up to 30 subjects with mCRPC to evaluate the safety and clinical activity of ADXS31-142 in combination with pembrolizumab (MK-3475).

Adverse events will be monitored from the time informed consent is obtained and graded in severity according to the guidelines outlined in the National Cancer Institute (NCI) Common Terminology Criteria for Adverse Events (CTCAE) Version (v) 4.03.

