5.2.1.1 Dose Selection

The rationale for the ADXS31-142 starting dose and the pembrolizumab (MK-3475) fixed dose are discussed in [Section 4.2.2](#). In Part A of the trial, the study was originally designed to include

dose-escalation/de-escalation with the decisions based on interim safety data review or pre-defined DLT criteria ([Section 5.2.1.1.1](#) – Dose Limiting Toxicity Criteria) and be based on 3 dosing intervals (below RP2D, at RP2D, or above RP2D) according to a mTPI with precalculated decisions that can easily be referred to ([Table 5](#)) [30, 31]. The TPI method would provide for exposure to fewer subjects to toxic doses above the MTD and yield similar probabilities in identifying the correct MTD, even when the sample size is matched [31]. A minimum of 3 subjects will be evaluated in each cohort before dose-escalation decisions are made. Table 5 consists of all the dose-escalation rules for the trial. If the toxicity rate of the currently used dose level is within the “under dosing” interval, the mTPI design recommended escalating the dose level; in the case of proper dosing, this design would recommend continuing at the current dose; for cases where toxicities indicate “over dosing”, the mTPI design would recommend de-escalating the dose level. As dosing was not determined based on this study alone, it was decided that escalation to 5×10^9 cfu or 1×10^{10} cfu would no longer be included in this study design. This is based on overall review of the safety data across the *Lm*-based program of clinical trials which determined that the starting dose would be 1×10^9 cfu. At the RP2D level in Part A up to 10 subjects may be enrolled. The Sponsor reserves the right to add additional subjects in order to further evaluate safety and tolerability. All decisions on dose-escalation and dose de-escalation will be made by the Sponsor only after discussions between Sponsor and Investigators have occurred.

Table 5 Dose Decisions for ADXS31-142 Monotherapy (Targeted DLT Rate = 25%)

The table is based on a sample size of 21 subjects. Two parameters epsilon1 and epsilon2 are set at default values [30] of 0.05. X-axis is number of subjects treated at current dose; y-axis is number of toxicities.

mTPI Decision Table

Sample Size = 21 ; Target Toxicity Probability = 0.25 ; epsilon 1 = 0.05 ; epsilon 2 = 0.05

ESCALATE STAY DE-ESCALATE UNACCEPTABLE

	1	2	3	4	5	6	7	8	9	10	11	12	13	14	15	16	17	18	19	20	21
0	E	E	E	E	E	E	E	E	E	E	E	E	E	E	E	E	E	E	E	E	

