1	D	D	S	S	S	S	E	E	E	E	E	E	E	E	E	E	E	E	E	E	
2		DU	D	D	S	S	S	S	S	S	S	S	S	E	E	E	E	E	E	E	
3		DU	DU	DU	D	S	S	S	S	S	S	S	S	S	S	S	S	S	E	E	
4			DU	DU	DU	DU	D	S	S	S	S	S	S	S	S	S	S	S	S	S	
5				DU	DU	DU	DU	DU	D	S	S	S	S	S	S	S	S	S	S	S	
6					DU	D	S	S	S	S	S	S	S	S							
7						DU	S	S	S	S											
8							DU	S	S												
9								DU													
10									DU												
11										DU											
12											DU										
13												DU									
14													DU								
15														DU							
16															DU	DU	DU	DU	DU	DU	
17																DU	DU	DU	DU	DU	
18																	DU	DU	DU	DU	
19																		DU	DU	DU	
20																			DU	DU	
21																				DU	

In the dose determining phase of Part B, dose-de-escalation will follow a modified 3+3 design as detailed in Section 5.2.1.1.3. At the RP2D level in Part B at least 6 subjects will be enrolled. All decisions on dose de-escalation will be made by the Sponsor only after discussions between Sponsor and Investigators have occurred.

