5.2.1.1.1 Dose Limiting Toxicity Criteria

The same DLT criteria will be utilized for study Part A and Part B. All toxicities will be graded using CTCAE v 4.03. The DLT window of observation will begin at the administration of the initial dose of ADXS31-142 and end 1 week following the second dose of ADXS31-142. The occurrence of any of the following toxicities will be considered a DLT, if judged by the investigator to be possibly, probably or definitely related to study treatment administration. Treatment modifications for DLT are shown in Table 8 and Table 9.

General:

1. Prolonged delay (>2 weeks) in initiating the second dose due to treatment-related toxicity
2. Missing the second dose of ADXS31-142 or pembrolizumab (MK-3475) as a result of AE(s) during the first cycle.

Hematologic:

1. Grade 4 hematologic toxicity.
2. Febrile neutropenia, defined as absolute neutrophil count (ANC) $< 1000/\text{mm}^3$ with a single temperature of >38.3 degrees C (101 degrees F) or a sustained temperature of ≥ 38 degrees C (100.4 degrees F) for more than 1 hour.
3. Grade 3 thrombocytopenia lasting >72 hours.
4. Grade 4 thrombocytopenia.

Non-Hematologic:

1. \geq Grade 3 non-hematologic toxicity, (excluding nausea, vomiting and/or diarrhea lasting <3 days and reversible with medical intervention).
2. Grade 3 non-hematologic laboratory value that does not downgrade to Grade 2 within 3 days after onset of the event despite optimal medical management (excluding transient Grade 3 laboratory value abnormalities reversible within 5 days and without medical intervention).
3. Listeremia: positive blood culture(s) along with persistent (for 72 hours post dose) symptoms consistent with listeremia (e.g., fever and muscle aches, often preceded by diarrhea or other gastrointestinal symptoms).
4. \geq Grade 3 flu-like or cytokine release symptoms that persist for >24 hours after ADXS31-142 administration despite symptomatic treatment (Refer to Section 7.2.3.2).

Subjects who experience a DLT at Dose Level -1 of 0.5×10^9 will be discontinued from study treatment. However, subjects who experience a DLT at DL 1 of 1×10^9 may be eligible to receive ADXS31-142 at a lower dose level for subsequent doses and cycles following discussion and agreement between the Investigator and Sponsor.

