5.2.1.2 Treatment Delays and Modifications

5.2.1.2.1 Pembrolizumab (MK-3475)

Adverse events (both non-serious and serious) associated with pembrolizumab (MK-3475) exposure may represent an immunologic etiology. These AEs may occur shortly after the first dose or several months after the last dose of treatment. Pembrolizumab (MK-3475) must be withheld for drug-related toxicities and severe or life-threatening AEs as per [Table 8](#) below.

Table 8 Dose Modification Guidelines for Drug-Related Adverse Events with Pembrolizumab (MK-3475)

Toxicity	Hold Treatment For Grade	Timing for Restarting Treatment	Discontinue Subject
Diarrhea/Colitis	2-3	Toxicity resolves to Grade 0-1.	Toxicity does not resolve within 12 weeks of last dose or inability to reduce corticosteroid to 10 mg or less of prednisone or equivalent per day within 12 weeks.
	4	Permanently discontinue	Permanently discontinue
Hypophysitis	2-4	Toxicity resolves to Grade 0-1. Therapy with pembrolizumab (MK-3475) can be continued while endocrine replacement therapy is instituted.	Toxicity does not resolve within 12 weeks of last dose or inability to reduce corticosteroid to 10 mg or less of prednisone or equivalent per day within 12 weeks.
AST, ALT, or Increased Bilirubin	2	Toxicity resolves to Grade 0-1	Toxicity does not resolve within 12 weeks of last dose.
	3-4	Permanently discontinue (see exception below) ¹	Permanently discontinue
Type 1 diabetes mellitus (T1DM) (if new onset) or Hyperglycemia	T1DM or 3-4	Hold pembrolizumab (MK3475) for new onset Type 1 diabetes mellitus or Grade 3-4 hyperglycemia associated with evidence of beta cell failure	Resume pembrolizumab (MK-3475) when subjects are clinically and metabolically stable.
Hyperthyroidism	3	Toxicity resolves to Grade 0-1	Toxicity does not resolve within 12 weeks of last dose or inability to reduce corticosteroid to 10 mg or less of prednisone or equivalent per day within 12 weeks.
	4	Permanently discontinue	Permanently discontinue
Hypothyroidism	1-4	Therapy with pembrolizumab (MK-3475) can be continued while thyroid replacement therapy is instituted	Therapy with pembrolizumab (MK-3475) can be continued while thyroid replacement therapy is instituted.
Infusion Reaction	3-4	Permanently discontinue	Permanently discontinue
Pneumonitis	2	Toxicity resolves to Grade 0-1	Toxicity does not resolve within 12 weeks of last dose or inability to reduce corticosteroid to 10 mg or less of prednisone or equivalent per day within 12 weeks.

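### The Part B expansion enrols about 24 more subjects after a 3+3 pass at no more than 2/6 DLTs, with no cumulative DLT count that would pause enrolment or reopen the RP2D; adding one is cheap, with modest benefit

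*Combined protocol and SAP*

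**What the plan says.** Section 5.2.1.1 confines the 3+3 rules to one stage: "In the dose determining phase of Part B, dose-de-escalation will follow a modified 3+3 design". Under Section 5.2.1.1.3, two or three DLTs in the first 3 subjects lead to de-escalation. Otherwise 3 more are treated, and a total of 0/6, 1/6 or 2/6 clears the dose. On the branch with no DLT in the first 3, "the current dose will be considered the RP2D and the trial will proceed to the dose expansion stage"; the branch with one DLT calls the cleared dose the recommended MTD and also goes on to expansion.

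The cohort-expansion paragraph of the same section then states: "It is planned to treat a total of approximately 30 subjects at the RP2D. Subjects will be enrolled on a rolling basis". Section 2.1.2 gives the expansion its purpose: "Further assessment of the RP2D will be explored in up to 30 subjects".

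The safety provisions that remain are these:
- Section 5.2.1.1.3 refers to an interim review: "Interim safety data review and/or DLTs observed at the first dose level will be used to determine the need for de-escalation". It is tied to the de-escalation step and has no count or schedule.
- Section 5.11, item 3, allows the trial to be terminated on the incidence or severity of adverse reactions, with no number attached.
- Sections 7.2.3.1 and 7.2.3.2 require SAEs and ECIs to be reported within 24 hours. ECIs include listeremia and any AE of Grade 3 or above.
- Tables 8 to 11 act on individual subjects.
- Section 8.2.3 lists DLTs among the data to be presented, without a decision rule.

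**The concern.** Part B's primary objective is the safety, tolerability and RP2D of the combination, and the expansion is meant to assess that RP2D further. Yet the plan does not say what DLT experience in subjects 7 to 30 would change the decision made on the first 6. If a poorly tolerated dose passes the 3+3 by chance, whether and when enrolment slows depends on unscheduled judgement. A stated count makes that review predictable and may spare a few subjects.

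**Working it through.** **Sample size.** Part A allows up to 21 subjects (Section 2.1.1) and Part B about 30 at the RP2D. 21 + 30 = 51, which reproduces the total in the Trial Summary. So the 30 includes the first 6, and 30 − 6 = 24 are still to come. The plan states no operating characteristics for the 3+3 or the expansion.

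**Information at clearance.** Clopper–Pearson 95% intervals are 0–46% for 0/6, 0.4–64% for 1/6 and 4–78% for 2/6.

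**Chance that the 3+3 passes the starting dose.** With true DLT rate p and q = 1 − p, and independent subjects:

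P(pass) = q³(1 − p³) + 3pq²(q³ + 3pq²)

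At p = 0.40: 0.216 × 0.936 + 0.432 × (0.216 + 0.432) = 0.202 + 0.280 = 0.482.
At p = 0.25: 0.4219 × 0.9844 + 0.4219 × 0.8438 = 0.415 + 0.356 = 0.771.

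**A candidate boundary.** Count DLTs at the RP2D including the first 6, and look after each further 3 subjects (n = 9, 12, …, 27). Call a review at the lowest count x for which P(rate > 25%) exceeds 0.95, where the rate has a Beta(1 + x, 1 + n − x) posterior, that is, a Beta(1,1) prior. The posterior probabilities are:

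| Boundary | 5/9 | 6/12 | 7/15 | 8/18 | 9/21 | 10/24 | 11/27 |
|---|---|---|---|---|---|---|---|
| P(rate > 25%) | 0.980 | 0.976 | 0.973 | 0.971 | 0.971 | 0.970 | 0.971 |

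One DLT fewer gives 0.920 to 0.932 at every look.

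**Operating characteristics.** An exact recursion starts from the distribution of DLT counts given a pass, adds Binomial(3, p) at each look and removes the paths that reach the boundary. Subjects spared = P(pass) × (30 − mean number treated given a pass). At p = 0.40 this is 0.482 × (30 − 24.43) = 2.7.

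| True DLT rate (assumed) | 3+3 passes | Review, given a pass | Spared, averaged over all trials | Same, with 6 more already dosed |
|---|---|---|---|---|
| 15% | 92% | 0.3% | 0.04 | 0.03 |
| 20% | 85% | 1.7% | 0.2 | 0.1 |
| 25% | 77% | 5.9% | 0.6 | 0.3 |
| 30% | 68% | 15% | 1.2 | 0.6 |
| 33% | 61% | 24% | 1.7 | 0.9 |
| 40% | 48% | 47% | 2.7 | 1.4 |
| 50% | 30% | 80% | 3.1 | 1.8 |

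The spared columns assume that every review ends enrolment and that nothing else would. They concern the starting dose only and count zero where the 3+3 has already rejected it. Given a pass, the mean number treated falls from 30 to 24.4 at 40% and to 19.4 at 50%.

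**If existing safeguards would stop enrolment anyway.** If they act at subject 24, the rule spares 1.4 at 40% and 1.8 at 50% (0.5 and 0.7 with the lag). If they act at subject 18, it spares 0.5 and 0.7 (under 0.1 with the lag).

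**The case against.** The strongest objection is that the sponsor would already know. The trial is open-label, and apart from the dose-delay items essentially every type of DLT reaches the sponsor within 24 hours as an ECI. Section 5.11 allows termination at any time, and the proposed count leads only to the same Sponsor–Investigator discussion. This stands as a limit on the benefit. It does not supply a number of DLTs among a number of subjects, and that is the gap. A reader might infer that the expansion has no safety stop at all; the provisions listed above rule that out.

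Second, the boundary is not the sponsor's. A reader might take it for the unacceptable-toxicity call of Table 5. The documents do not support that. Section 5.2.1.1 gives the target, sample size and epsilon values, but neither a prior nor a 0.95 cut-off, and it labels the table for monotherapy. The extracted rows are misaligned. If they are shifted to remove impossible cells, 3/5 (posterior 0.962) reads as unacceptable while 5/10 (0.966) reads only as de-escalate, so no single cut-off on this posterior reproduces the table. It also ends at 21 subjects. This objection stands in full: the boundaries are a proposal.

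Third, lag is unavoidable. Enrolment is rolling, and the DLT window runs from the first dose to its "end 1 week following the second dose of ADXS31-142", about four weeks when the second dose falls at Week 4. This also stands, and the last column of the table reflects it.

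Fourth, the context is reassuring: the combination does not go above the Part A dose, Section 9.4.2 reports only mild to moderate infusion-related effects for the related construct in over 200 subjects, and Section 4.2.2.2 reports no DLTs in pembrolizumab's own escalation. That does not establish the safety of the combination, but it is a reason not to rest the case on true rates of 40–50%.

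**Conclusion.** The point holds as a cheap, low-priority improvement. After a pass at no more than 2/6, the visible text contains no cumulative DLT count that pauses the expansion or reopens the RP2D. The design figure in Section 2.1.2 is not shown, so this is a statement about the readable text; Sections 5.2.1.1.3 and 5.11 and the visible parts of Section 8, where such a rule would sit, contain none.

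The gain is close to zero at true rates of 15–20% and about 3 subjects at most at 50%. It roughly halves with a 6-subject lag and shrinks further if existing safeguards act. These figures rest on independent DLTs, assumed true rates and a 25% threshold, because the documents define no unacceptable rate for the combination.

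Three stronger inferences should be resisted:
- The 3+3 cut-off itself is not shown to be wrong; a wide interval at 6 subjects is common to any 3+3.
- The rule would not reliably catch a toxic dose. Given a pass, it misses about half of cases at 40% and about three quarters at 33%.
- A DLT count says nothing about toxicity after the window, and Section 5.2.1.2.1 warns of pembrolizumab events: "These AEs may occur shortly after the first dose or several months after the last dose of treatment".

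**What to change.** In Section 5.2.1.1.3 (Cohort Expansion), cross-referenced in Section 5.11, state that DLTs are counted cumulatively at the RP2D, including the first 6 subjects. After each further 3 subjects complete the DLT window, new enrolment pauses for the existing Sponsor–Investigator review if the count reaches 5/9, 6/12, 7/15, 8/18, 9/21, 10/24 or 11/27. The decision to resume, reduce the dose or stop stays with that group.

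Describe the basis openly as P(DLT rate > 25%) above 0.95 under a Beta(1,1) prior, and do not attribute it to Table 5. A first look at 4/9 should not be used, since its posterior probability is 0.922. The sponsor should first confirm 25% for the combination or replace it; a different threshold means recalculating the seven entries.

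The cost is one paragraph and a seven-entry table, using DLT data already collected, with no added subjects, visits or committee. The downside is an occasional unneeded pause after a 3+3 pass: 0.3% of cases at a true 15%, 1.7% at 20% and 5.9% at 25%.
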